3.3.3 Rationale for Antibody Assay Assessments

As with all therapeutic proteins, there is potential for immunogenicity. In the case of GH, antibodies with GH binding capacities below 2 mg/L have not been associated with growth attenuation (*refer to the USPI for Nutropin AQ*). In a very small number of patients treated with Nutropin AQ, where binding capacity was above 2 mg/L, interference with growth response was observed. In clinical studies of pediatric patients who were treated with Nutropin or Nutropin AQ for the first time, antibodies with binding capacities ≥ 2 mg/L were not observed in any patients at 6 months *or* 15 months for Nutropin AQ, respectively (refer to the USPI for Nutropin AQ).

In this study, all serum samples taken for immunogenicity assessments will be analyzed in an anti-GH antibody screening assay. Any samples positive for anti-GH antibody with a titer > 2.4 mg/L will *then* be analyzed in an anti-GH neutralizing antibody assay and an anti-GH antibody binding capacity assay. Neutralizing antibody assays are an additional method for assessing anti-therapeutic antibodies that can result in changes in the toxicology, pharmacokinetics, and efficacy of biotechnology-derived pharmaceuticals. Growth attenuation due to the development of neutralizing anti-GH antibodies is rare and, when reported, usually occurs in patients with mutations in the GH encoding gene (Schwarz et al. 1987; Cogan and Phillips 2006). When this rare event occurs, the growth response in the first 3–6 months is followed by a rapid decline in annualized

Nutropin AQ (Somatropin [rDNA origin])—Genentech, Inc. 26/Protocol ML29543, Version 2

Clinical Study Report: Nutropin AQ (Somatropin)—Genentech, Inc. 375/CSR ML29543

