growth velocity to below pretreatment rates. Conversely, in those patients without a genetic mutation who develop antibodies, the binding capacity is usually low, and a functional effect on growth has very rarely been detected (Buzi et al. 1989; Pirazzoli et al. 1995). GH-1 mutation testing may be performed at the discretion of the investigator and will not be conducted as part of the protocol. Data from this study will be used to determine if the immunogenicity profile of Nutropin AQ v1.1 produced by the new manufacturing process is different from the original product. This study will also include outcome measures to evaluate the growth of GHD children being treated with Nutropin AQ v1.1 to determine if any variations in growth are associated with antibody development.

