4.6 PATIENT, TREATMENT, STUDY, AND SITE DISCONTINUATION

4.6.1 Patient Discontinuation

Patients have the right to voluntarily withdraw from the study at any time for any reason. In addition, the investigator has the right to withdraw a patient from the study at any time. Reasons for withdrawal from the study may include, but are not limited to, the following:

- Patient withdrawal of consent at any time
- Any medical condition that the investigator or Sponsor determines may jeopardize the patient's safety if he or she continues in the study
- Investigator or Sponsor determines it is in the best interest of the patient
- Patient non-compliance, specifically defined as: refusal to allow for serum draws for antibodies; failure to adhere to study visit schedule; failure to comply with GH administration by giving less than 85% of daily injections over each 3-month interval

Nutropin AQ (Somatropin [rDNA origin])—Genentech, Inc. 33/Protocol ML29543, Version 2

• Development of growth failure with velocity decrease to below pretreatment velocity

Every effort should be made to obtain information on patients who withdraw from the study. The primary reason for withdrawal from the study should be documented on the appropriate eCRF. However, patients will not be followed as part of the study for any reason after consent has been withdrawn. Patients who withdraw from the study prematurely will not be replaced.

4.6.2 Study Treatment Discontinuation

Patients who experience a protocol-defined adverse event may be discontinued from treatment (see Section 5.1.1). Patients who discontinue study treatment prematurely will be asked to return to the clinic for an early discontinuation visit and may undergo final study assessments. The primary reason for premature study treatment discontinuation should be documented on the appropriate eCRF. Patients who discontinue study treatment prematurely may remain in the study and continue to be followed per the schedule of assessments for sample collection, reporting of adverse events, and height and weight measurements.

4.6.3 Study and Site Discontinuation

The Sponsor has the right to terminate this study at any time. Reasons for terminating the study may include, but are not limited to, the following:

- The incidence or severity of adverse events in this or other studies indicates a potential health hazard to patients
- Patient enrollment is unsatisfactory

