6.3.1 Primary Endpoint

The primary endpoint for this study is the proportion of patients who develop anti-GH antibodies after *initiating* treatment with Nutropin AQ v1.1.

6.3.2 Secondary Endpoints

The secondary endpoints for this study are as follows:

- Proportion of patients who exhibit growth attenuation (defined as initial growth response greater than pretreatment velocity followed by reduction in growth response to below the pretreatment velocity in the subsequent 6- to 12-month treatment period or reaching ≤2 cm per year)
 - Cross tabulation between growth attenuation status (i.e., with or without) and anti-GH antibody status (i.e., positive or negative) will be provided for any

Nutropin AQ (Somatropin [rDNA origin])—Genentech, Inc.

48/Protocol ML29543, Version 2

antibody and for neutralizing anti-GH antibody, respectively, at each visit. Similar tables will also be provided for patients who had at least one positive anti-GH antibody (anti-GH antibody and neutralizing antibody, respectively) at any follow-up visit against those who never developed antibody after treatment.

- Proportion of patients with neutralizing antibody among those who had positive anti-GH antibody
 - This analysis will be summarized by visit, as well as *cumulatively*, for patients who had detectible anti-GH antibody at any post-baseline visit, as well as those who *remained negative throughout the study*.
- Annualized 6- and 12-month growth velocities and height SDS will be summarized separately for patients who were anti-GH antibody-positive at any post-baseline follow-up visit and those who were anti-GH antibody-negative at all visits (including baseline). Graphic displays of the individual patient growth patterns along with the longitudinal antibody profile over the course of the study will be prepared. Patients who enter puberty during the study period will be included up to the last visit at which they were determined to be prepubertal.

Additional analyses deemed appropriate for assessing immunogenicity will be described in the Statistical Analysis Plan.

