4.4.1 Primary Outcomes Endpoint

The primary endpoint for this study is the proportion of patients who develop anti-GH antibodies (i.e., with positive anti-GH antibody screening assay result) after initiating treatment with Nutropin AQ v1.1.

Among all patients with at least one post-baseline screening assay result, the number and percentage of patients who have at least one positive anti-GH antibody screening assay result at any post-baseline visit will be presented. The Clopper-Pearson exact 95% Cls for the percentage will also be provided.

An anti-GH antibody screening assay result is considered positive if the titer is \geq 1.0 mg/L.

4.4.2 Secondary Outcomes Endpoints

The secondary endpoints for this study are as follows:

- Proportion of patients who exhibit growth attenuation is defined as
 - (1) initial growth response greater than pretreatment velocity followed by reduction in growth response to below the pretreatment velocity in the subsequent 6- to 12month treatment period

or

(2) reaching \leq 2 cm per year at any scheduled visit: Month 3, 6, 9, or 12

Please note that for criteria (1), the initial growth response occurs as early as Month 3 and growth attenuation status at post-baseline visit will be evaluated at Months 6, 9, or 12.

The growth response is based on the annualized growth velocity defined as (height - baseline height)/ (date of height assessment – date of baseline)*365.25 at any post-baseline visit.

Pretreatment growth velocity is defined as (Baseline height – last historical height) / (date of baseline – date of last historical height)*365.25

Growth attenuation status at post-baseline visit Tk (=Month 6, Month 9 or Month 12 for k=6, 9, or 12) will be classified as follows:

Yes: If growth velocity at Tk< pretreatment growth velocity and there is Tj < Tk with growth velocity at Tj > pre-treatment growth velocity, for j<k, and k=6, 9, or 12 or growth velocity \leq 2 cm per year at any scheduled visit: Month 3, 6, 9, or 12 **No:** Otherwise.

Nutropin AQ (Somatropin [rDNA origin])—Genentech, Inc. 9/Statistical Analysis Plan ML29543 • 2x2 cross tabulation (with frequencies and percentages) of growth attenuation status (yes or no) and anti-GH antibody status (positive or negative) will be provided for each antibody assay at each visit (Month 6, 9, and12).

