Similar tables of growth attenuation status (yes at any visit from Month 6 to Month 12) and anti-GH antibody status for those who had a positive antibody assay at any follow-up visit (negative at baseline) and those who remained negative throughout the study (including baseline) will also be provided.

- Proportion of patients with neutralizing anti-GH antibody (Nab positive) among those who had positive anti-GH antibody. This analysis will be summarized by visit, as well as cumulatively, for patients who had detectible anti-GH antibody (ATA) at any post baseline visit (with negative antibody assay at baseline), as well as those who remained negative throughout the study (including baseline).
- Annualized 6- to 12- month growth velocities and height SDS. These variables will be summarized separately for patients who were anti-GH antibody-positive at any post-baseline follow-up visit (negative at baseline) and those who were anti-GH antibody-negative at all visits (including baseline).

The difference between the annualized 6- and 12- month growth velocities will be presented separately for patients who were anti-GH antibody-positive at any post-baseline visit and those who were anti-GH antibody-negative at all visits (including baseline).

Graphic displays of the individual patient growth patterns (growth velocity); along with the longitudinal antibody profile over the course of the study will be prepared.

For the above analyses, if there is any patient who appears to have positive anti-GH antibody at baseline, they will be summarized separately from the other groups.

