4.7 MISSING DATA

Missing data will not be imputed for efficacy outcome measures. All available assessments will be reported with associated number of observations. If a patient discontinues study medication before the end of the 1-year treatment period, their growth rate will be computed for the last 3-month interval visit and used in the calculation of mean growth for that time interval only.

Nutropin AQ (Somatropin [rDNA origin])—Genentech, Inc. 13/Statistical Analysis Plan ML29543

There are two criteria for defining growth attenuation: (1) initial growth response greater than pretreatment velocity followed by reduction in growth response to below the pretreatment velocity in the subsequent 6- to 12-month treatment period, or (2) reaching \leq 2 cm per year at any scheduled visit: Month 3, 6, 9, or 12.

For criteria (1), if the pretreatment velocity is missing then growth attenuation is missing. Otherwise,

- 1. If patient discontinued < month 3, the growth attenuation will be missing because the initial growth response cannot be determined for criteria (1).
- 2. If patient discontinued \geq month 3 and < month 6, then:
 - a. If the height on Month 3 is missing, the growth attenuation will be missing because the initial growth response cannot be determined.
 - b. If the height on Month 3 is non-missing, the initial growth response can be determined but the growth attenuation cannot be determined because there is no Month 6 visit to determine the reduction in growth response to below the pretreatment velocity.
- 3. If patient discontinued ≥ month 6, the growth attenuation will be calculated based on the original definition.

For safety analyses, incomplete onset dates for adverse events and concomitant medications will be imputed according to the following algorithm:

- If the day is missing, the 1st of the month will be used.
- If the day and month are missing, January 1st will be used.

In cases where the imputation of the start/onset date leads to adverse events or concomitant medications occurring before treatment start, the start date will be set to the treatment start date.

Incomplete end dates for non-ongoing adverse events or concomitant medications will be imputed according to the following algorithm:

- If the day is missing, the last day of the month will be used.
- If the day and month are missing, December 31st will be used.

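### SAP 4.4.2 judges growth attenuation on velocity averaged from baseline, so a child who stops growing at Month 6 is classed 'No' at Month 12 if earlier velocity was at least twice pretreatment velocity and above 4 cm/yr

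*SAP*

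**What the plan says.** Protocol 6.3.2 defines growth attenuation as an initial response above pretreatment velocity "followed by reduction in growth response to below the pretreatment velocity in the subsequent 6- to 12-month treatment period", or a velocity of 2 cm/yr or less. It gives no formula. Protocol 3.3.3 describes the expected course of antibody-related attenuation: "When this rare event occurs, the growth response in the first 3–6 months is followed by a rapid decline in annualized" "growth velocity to below pretreatment rates".

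SAP 4.4.2 supplies the formula, "annualized growth velocity defined as (height - baseline height)/ (date of height assessment – date of baseline)*365.25 at any post-baseline visit", and uses it in both limbs:

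- Limb (1): 'Yes' at Month 6, 9 or 12 if the velocity at that visit is strictly below pretreatment velocity and the velocity at an earlier visit was above it.
- Limb (2): 'Yes' if velocity is 2 cm/yr or less at Month 3, 6, 9 or 12.

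This status fills the by-visit cross-tabulations with antibody status. It also fills the cumulative ones: "Similar tables of growth attenuation status (yes at any visit from Month 6 to Month 12) and anti-GH antibody status". For children who discontinue at or after Month 6, SAP 4.7 says "the growth attenuation will be calculated based on the original definition".

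**The concern.** The protocol asks how the child grows after the initial response. The SAP answers with an average over the whole time since baseline. The early response that the definition requires therefore props up the later value, and the better that response was, the harder a later loss is to see. The 2 cm/yr limb is no safeguard, because it uses the same average.

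Growth attenuation in association with antibodies is the clinical-impact part of the study's objective (Protocol section 2). Protocol 3.3.3 expects such cases to be rare, so one or two misclassified children could empty the cell that matters. A reader of that cell could not tell absence of effect from an artefact of the formula.

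**Working it through.** **Inputs from the documents.** The velocity formula and both limbs (SAP 4.4.2); nominal Month 6 = Day 180 and Month 12 = Day 360, with windows Day 136–225 and Day 316–405 (SAP Table 2); visit tolerance ±3 days (Protocol Appendix 1). The plan gives no figure on this point to reproduce.

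**Algebra.** Let v0 be pretreatment velocity, v1 > v0 the velocity until onset at month m, and u the velocity afterwards. At nominal visits

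V12 = (m·v1 + (12 − m)·u)/12.

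The child is 'No' on the Month 12 value if V12 ≥ v0 and V12 > 2.

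*Complete arrest (u = 0):* 'No' if v1 ≥ (12/m)·v0 and v1 > 24/m.

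*Fall to half of pretreatment (u = v0/2):* 'No' if v1 ≥ v0·(12 − (12 − m)/2)/m, unless the average is 2 cm/yr or less.

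| Onset | Arrest is 'No' if | Fall to half of v0 is 'No' if |
|---|---|---|
| Month 6 | v1 ≥ 2 × v0 and v1 > 4 | v1 ≥ (9/6) = 1.5 × v0 |
| Month 4.5 | v1 ≥ 2.67 × v0 and v1 > 5.3 | v1 ≥ (8.25/4.5) = 1.83 × v0 |
| Month 3 | v1 ≥ 4 × v0 and v1 > 8 | v1 ≥ (7.5/3) = 2.5 × v0 |

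Example with assumed values: v1 = 10, v0 = 4, arrest at Month 6. V9 = 10 × 180/270 = 6.67 and V12 = 10 × 180/360 = 5.0, so the child is 'No' at Months 6, 9 and 12 after six months without growth. Coding the SAP rule and comparing it with the Month 6 condition over 17,808 (v1, v0) pairs gave no mismatch.

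The factor 2 is Month 12 day/Month 6 day. Within ±3 days it runs from 357/183 = 1.95 to 363/177 = 2.05. Across the Table 2 windows it runs from 316/225 = 1.40 to 405/136 = 2.98.

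**Size, under assumptions.** Assumed: mean v0 4, 4.5 or 5 cm/yr (SD 1); mean v1 8, 9 or 10 cm/yr (SD 2); height error SD 0.2, 0.3 or 0.5 cm; historical height 12 months before baseline; abrupt change at onset. There were 200,000 simulated children per cell, keeping those with v1 > v0. The SAP rule is 'Yes' at any of Months 6, 9 or 12, with limb (2) at Months 3, 6, 9 and 12. Ranges are over the 27 cells.

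| Flagged | Onset Month 6 | Month 4.5 | Month 3 |
|---|---|---|---|
| Arrest, SAP rule | 25–70% | 54–89% | 82–99% |
| Arrest, Month 6–12 interval | 98–100% | 98–100% | 98–100% |
| Fall to half, SAP rule | 6–37% | 18–57% | 49–82% |
| Fall to half, Month 6–12 interval | 86–99.5% | 84–99% | 82–99% |
| Arrest, SAP rule, child leaves at Month 9 | 6–35% | 25–66% | 63–93% |

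Sensitivity for arrests, by onset at Months 6, 4.5 and 3:

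- Visit days uniform over the Table 2 windows: SAP rule 25–69%, 55–89% and 82–97%; interval test 95–100%.
- Correlation of 0.5 between v0 and v1: SAP rule 18–79%, 56–94% and 86–100%; interval test 98–100%.
- Historical height only 6 months before baseline: SAP rule 26–68%, 51–86% and 76–98%; interval test 97–100%.

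**The case against.** **Other outputs already carry the information.** "The difference between the annualized 6- and 12- month growth velocities will be presented separately" by antibody status. With equal intervals the later velocity is exactly 2 × V12 − V6, so an arrest at Month 6 shows as a halving. There are also individual growth plots, height SDS by antibody status, height listings and reasons for not completing, and with about 80 children individual review is practicable. This lowers the risk but leaves the Yes/No tables unchanged. The last-3-month growth rate in SAP 4.7 feeds mean growth only.

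**The protocol gives no formula, and interval velocity is noisier.** Both are true. But the protocol's wording describes later growth, which an average from baseline does not isolate.

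**More false flags where true cases may be near zero.** This stands as a real cost. Suppose 62 children are evaluable (80 less 22.5%: 12.5% dropout plus 10% puberty) and all truly stay at or above pretreatment velocity. In the central cell (v0 4.5, v1 9, error 0.3), with later velocity 85% or 70% of v1, the combined status gives 62 × 3.9% = 2.4 or 62 × 7.9% = 4.9 spurious 'Yes'. The SAP rule gives 62 × 1.2% = 0.7 or 62 × 0.6% = 0.4. The new table should therefore stand beside the existing one and not replace it.

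**A Month 6–12 velocity is itself an average.** Also true. For arrest at Month 9 it equals v1/2, and the same factor of 2 returns. The combined status then flags about 25–70%, against 3–24% for the SAP rule. The 98–100% holds only for onset by Month 6, which is the response period in Protocol 3.3.3. Later onsets are improved but not solved.

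**Early leavers.** Protocol 4.6.1 lists "Development of growth failure with velocity decrease to below pretreatment velocity" among the reasons for withdrawal. Such a child may have no Month 12 height, and a Month 12 test cannot recover that case.

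**Conclusion.** The concern holds and should be fixed. The thresholds follow from the SAP formula alone: at nominal visits, complete arrest at Month 6 is 'No' at Month 12 when v1 ≥ 2 × v0 and v1 > 4 cm/yr. The detection rates depend on the assumed velocities, measurement error and abrupt onset, so how many children in this trial would be misclassified is unknown. The loss is large for onset at Months 4.5 to 6 and modest for complete arrest at Month 3. The endpoint is secondary and descriptive, with no hypothesis test planned. What is at risk is the reading of the attenuation-by-antibody tables.

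**What to change.** **SAP 4.4.2.** Keep the current status, including the 2 cm/yr limb at Months 3, 6, 9 and 12, and all by-visit tables. With arrest at Month 3, 26–65% of children are already 'Yes' by Month 6, so the current status must not be dropped. Add a Month 12 interval test:

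later velocity = (Month 12 height − Month 6 height)/(days between) × 365.25.

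It is met if (a) baseline-to-Month 3 or baseline-to-Month 6 velocity exceeds pretreatment velocity and later velocity is below it, or (b) later velocity is 2 cm/yr or less.

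Present the any-follow-up-visit antibody table twice: with the current status, and with 'Yes' if either the current status or the interval test is met. A child already 'Yes' before leaving stays 'Yes' in both. In the second table, a child who is not 'Yes' on the current status and lacks a prepubertal Month 6 or Month 12 height goes in a separate row for interval test not evaluable, not under 'No'. List that child's Month 6-to-last-height velocity and reason for leaving. State that the test is aimed at onset by Month 6 and is weaker for later onset.

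**SAP 4.7.** Keep the present rules. Add that the interval test is missing without both heights, and that part (a) is missing without pretreatment velocity. List the days between the two heights, and mark any child who stopped study drug before the Month 12 height but stayed in the study (Protocol 4.6.2 allows this).

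**Cost.** Wording and programming only, since the heights are already scheduled. On the assumptions above, 'Yes' on either test catches 98–100% of arrests and 87–99.5% of falls to half with onset by Month 6. False flags among children who truly stay at or above pretreatment velocity are:

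| Later velocity as % of v1 | Combined | SAP rule |
|---|---|---|
| 100% | 0.3–13% | 0.2–9% |
| 85% | 0.6–17% | 0.1–8% |
| 70% | 2–23% | 0–6% |

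Precision depends on spacing, which Table 2 allows to run from 316 − 225 = 91 to 405 − 136 = 269 days. With SE = √2 × 0.3 × 365.25/days, the velocity SE is 1.70 cm/yr at 91 days, 0.86 at 180 and 0.58 at 269. That is why the listing should show the days.

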4.1.1 Inclusion Criteria

Patients must meet the following criteria for study entry:

- Signed Informed Consent/Assent Form
 - The parent(s)/guardian(s) must be willing to give written informed consent; and
 - The child may be required to give written informed assent (if able, and dependent on state/Institutional Review Board [IRB] requirements)
- Willing to adhere to the visit schedules and meet study requirements
 - For patients below the legal age of consent, both child and parent must be able to adhere to dose and visit schedules and meet study requirements.
- Ability to comply with study assessments for the full duration of the study (1 year)
- Male or female patients age \geq 3 years and <14 years. The patient may be 14 years old exactly on the day of the first dose of study treatment.
- Bone age ≤9 years (females) or ≤11 years (males) as determined by X-ray of the left hand and wrist using Greulich and Pyle method and obtained within the 12 months prior to enrollment
- Prepubertal (Tanner I) males and females by physical exam
- Diagnosis of GHD (stimulated GH < 10 ng/mL) by two standard pharmacologic tests obtained up to 12 months prior to informed consent/assent.
 - Acceptable GH stimulation tests include: insulin tolerance test (considered two tests if done sequentially with arginine); arginine stimulation test (considered two tests if done sequentially with insulin); glucagon stimulation test; clonidine stimulation test; L-dopa stimulation test; L-dopa+inderal stimulation test (considered one test if done together).
- Normal thyroid function test within the 12 months prior to informed consent/assent
- Normal CBC within the 12 months prior to informed consent/assent
- Documentation of prior height and weight measurements, with height standard deviation score (SDS) ≤ −1.5 (≤5th percentile) for idiopathic isolated GHD patients

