4.5.2 Medical History and Demographic Data

Medical history includes clinically significant diseases, surgeries, prior height and weight measurements, and all prescription medications used by the patient in the 30 days prior to the screening visit.

Demographic data will include date of birth, sex, and self-reported race/ethnicity.

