4.3 ANALYSIS OF TREATMENT GROUP COMPARABILITY

This is a single-arm study therefore only descriptive statistics will be provided; no treatment group comparison will be performed.

Clinically important demographic and disease characteristics at baseline will be summarized overall. Summaries will be produced for the ITT population.

Continuous variables will be summarized by the number of non-missing observations, mean, standard deviation, median, minimum and maximum values. Categorical variables will be summarized using numbers and percentages of patients in each category; unknown or missing will be included as a separate category.

The variables to be summarized include but are not limited to the following:

• Demographics: sex, ethnicity, race(s), age (continuous).

Nutropin AQ (Somatropin [rDNA origin])—Genentech, Inc. 7/Statistical Analysis Plan ML29543 Baseline characteristics: height, weight, height standard deviation score (SDS) (continuous and categorized as ≤ -3, >-3 to ≤ -2, >-2 to ≤ -1, >-1), pre-treatment growth velocity, and prepubertal Tanner stage < 1 (yes or no). See Appendix 3 for the SAS macros for the calculation of normal height SDS (z-scores) for this study.

Pre-treatment growth velocity is calculated from the baseline and last historical height measurements as: 365.25 × (Baseline height – last historical height)/(date of baseline height – date of last historical height)

- Disease-related characteristics: birth weight, bone age, diagnosis of Turner syndrome.
- Baseline antibody testing (anti-growth hormone antibody screening assay (ATA), anti-growth hormone neutralizing antibody assay (Nab) and anti-growth hormone antibody binding capacity assay (ABC).
- Medical history in specific categories.
- Historical Laboratory Results on GH stimulation test (maximum GH level, insulin level, L-Dopa level), thyroid function test (free T4, total T4, TSH) in 12 months prior to informed consent/assent.
- Screening/Baseline physical examination results, including presence of hip or knee pain, fundoscopic examination and appearance of spine.

Subject listings on demographics, baseline characteristics, medical history, screening physical examination and historical laboratory measurements will be provided.

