4.4 OUTCOME ANALYSES

Outcome analyses will be performed on the modified ITT population. In the analyses related to growth attenuation, growth velocity and height SDS, patients who enter puberty during the study period will be included only up to the last visit at which they were determined to be prepubertal.

The study windows listed below in Table 2 (based on visit dates) will be used:

Visit	Target Day	Window
Screening/Baseline	Day -28 to -1	Day -28 to 1
Month 1	Day 30	Day 2 to 60
Month 3	Day 90	Day 61 to 135
Month 6	Day 180	Day 136 to 225
Month 9	Day 270	Day 226 to 315
Month 12	Day 360	Day 316 to 405

Table 2 Study Windows

If more than one assessment is measured within the same visit window, then the record with the latest visit date (from baseline) will be used for that visit window.

Nutropin AQ (Somatropin [rDNA origin])—Genentech, Inc. 8/Statistical Analysis Plan ML29543

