4.6.3 Laboratory Data

Individual serum drug concentration / GH concentration, immunogenicity (anti-GH antibody screening, neutralizing anti-GH antibody, and antibody binding capacity) assay results will be listed, sorted by patient and visit.

The GH concentration at each visit will be summarized for patients in modified ITT population who have serum blood sample assayed for study drug/GH concentration. Descriptive statistics will include the number of observations (n), mean, standard

Nutropin AQ (Somatropin [rDNA origin])—Genentech, Inc. 12/Statistical Analysis Plan ML29543

deviation, coefficient of variation, median, minimum, maximum, geometric mean, and geometric coefficient of variation.

The serum concentration-time profiles in semi-logarithmic (log/linear) scales, growth velocity time-profile and antibody status (anti-GH antibody, neutralizing anti-GH antibodies, antibody binding capacity) for individual patient will be presented.

Patients who became pregnant during the study will be listed with available pregnancy test results.

4.6.4 Vital Signs

Height, weight and their change from baseline values will be summarized in terms of mean, standard deviation, median, minimum, and maximum at each visit. The average of three measurements of height at each visit will be used for analysis and computation of the height SDS and growth velocity. The height and weight data will also be presented in a data listing.

4.6.5 **Previous and Concomitant Medications**

All verbatim terms for medications recorded in the case report form (CRF) will be coded by preferred term and an anatomic therapeutic class (ATC) term using International Nonproprietary Name (INN) drug terms and procedures. Concomitant medications and prior medications will be summarized separately, based on the safety population, with number (percentage) of patients in each ATC class and preferred drug name. Prior and concomitant medications will also be presented in data listings.

Prior and concomitant medications are defined as follows:

- Prior medication is defined as any medication with start date before the first day of study drug, or checked to be prior to first study drug administration date, or medication with start date missing.
- Concomitant medication/treatment is any medication/treatment with start date on or after the initial dosing of study treatment, whichever occurs first.

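### Pretreatment velocity rests on the last historical height with no minimum interval to baseline, so a short gap can hide or create growth attenuation under criterion (1)

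*SAP*

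**What the plan says.** SAP 4.4.2 defines the reference: "Pretreatment growth velocity is defined as (Baseline height – last historical height) / (date of baseline – date of last historical height)*365.25". SAP 4.3 gives the same formula for the baseline tables: "Pre-treatment growth velocity is calculated from the baseline and last historical height measurements as", followed by the annualized difference.

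Criterion (1) in SAP 4.4.2 uses this value twice. A child is a Yes if the velocity at Month 6, 9 or 12 is below it and an earlier on-treatment velocity was above it. Both comparisons are strict. On-treatment velocity is cumulative from baseline. Criterion (2), a velocity of 2 cm/yr or less, does not use the reference.

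On the historical height itself, Protocol 4.1.1 requires "Documentation of prior height and weight measurements, with height standard deviation score (SDS") at or below −1.5 for idiopathic isolated deficiency, and Protocol 4.5.2 collects the heights as history: "Medical history includes clinically significant diseases, surgeries, prior height and weight measurements". Neither gives a date range or spacing. By contrast, Protocol 4.1.1 puts a 12-month window on the stimulation tests, thyroid function, blood count and bone age.

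For study visits, SAP 4.6.4 states: "The average of three measurements of height at each visit will be used for analysis". No such rule covers chart heights. SAP 4.7 deals only with absence: "For criteria (1), if the pretreatment velocity is missing then growth attenuation is missing".

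**The concern.** A velocity is a difference of two heights divided by time, so the shorter the interval, the more any reading error is inflated. If a child has several prior heights, choosing the last one chooses the shortest interval and therefore the largest reading error.

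The error can act in two directions. A reference that is far too low is never undercut, and one that is far too high is never exceeded at first; both hide true attenuation. A reference pushed up into the child's on-treatment range turns the ordinary waning of response into a false Yes.

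Growth attenuation is how the study judges whether antibodies matter clinically. Protocol 3.3.3 says: "Growth attenuation due to the development of neutralizing anti-GH antibodies is rare". With few true cases expected, one or two misclassified children could change the count.

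**Working it through.** The documents give no height-error figure and no calculation for this endpoint, so there is no planned figure to reproduce.

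**Inputs.** From the SAP: the formula and the criterion (1) rule (4.4.2), and the averaging of three readings at study visits (4.6.4). Assumed: reading-error SD e = 0.3 cm (range 0.2–0.5), one historical reading, and the growth paths below.

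**Step 1: precision of the reference (no growth assumption needed).**
SD = √(e² + e²/3) × 12/gap in months. For e = 0.3: √(0.09 + 0.03) = 0.346 cm. The chance of being off by more than 1 cm/yr is 2 × (1 − Φ(1/SD)).

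| Gap (months) | SD, cm/yr (range for e = 0.2–0.5) | Off by more than 1 cm/yr (range) |
|---|---|---|
| 1 | 0.346 × 12 = 4.2 (2.8–6.9) | 81% (72–88%) |
| 3 | 0.346 × 4 = 1.4 (0.9–2.3) | 47% (28–67%) |
| 6 | 0.346 × 2 = 0.7 (0.5–1.2) | 15% (3–39%) |
| 12 | 0.346 × 1 = 0.35 (0.2–0.6) | 0.4% (0–8%) |

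The Month 6 velocity compared with it has SD √(e²/3 + e²/3) × 12/6 = √0.06 × 2 = 0.49 cm/yr (0.33–0.82). At a 3-month gap the reference is nearly three times as noisy (1.39/0.49 = 2.8).

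**Step 2: effect on the Yes/No status.** The criterion (1) rule was simulated with error in every height and the baseline error shared between the reference and the on-treatment velocities. True pretreatment velocity was 4.0, 4.5, 5.0 or 5.5 cm/yr. Paths are cumulative velocities in cm/yr at Months 3, 6, 9 and 12.

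- Attenuating: 9/6/4.3/3.5 and 9/6/4/3. The second has height gains of 2.25, 3.0, 3.0 and 3.0 cm, that is, no growth after Month 6. A third path, 9/5.5/3.6/2.5, was left out: its gains are 2.25, 2.75, 2.70 and 2.50 cm, so the child would lose height.
- Waning normally, no attenuation: 10/9.5/9/8.5, 9/8.5/8/7.5 and 9/8.2/7.5/7.

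| Gap (months) | True attenuation missed, e = 0.3 | False Yes, e = 0.3 |
|---|---|---|
| 1 | 50–59% | 6–15% |
| 3 | 8–37% | 0.1–13% |
| 6 | under 1% to 27% | 0–3% |
| 12 | 0–15% | 0–0.1% |

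Over e = 0.2–0.5 the missed range widens to 32–73%, 1–48%, 0–37% and 0–27%, and the false Yes range to 3–17%, 0–17%, 0–12% and 0–4%.

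**Step 3: what drives the upper ends.** The highest missed rates come from one borderline child: pretreatment 4.0, path 9/6/4.3/3.5. The height gain is 3.0 cm by Month 6 and 3.5 cm by Month 12, so growth in the second half-year is 0.5 cm, or 1 cm/yr. The cumulative Month 12 velocity is still 3.5, only 0.5 below the reference. The cumulative definition narrows that margin, so the gap is not the sole cause.

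**The case against.** **How often it happens is unknown.** Nothing in the documents shows that gaps of 1 month, or even 3, occur. This stands; the 1-month figures show what the rule permits, not what the trial will see.

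**Screening heights.** A reader might infer that the screening height could serve as the last historical height, which would make gaps of 28 days or less routine. The documents do not support that. Screening height has its own row in the schedule of assessments and falls in the joint Screening/Baseline window of SAP Table 2, which has its own rule ("If more than one assessment is measured within the same visit window", the latest is used). Prior heights are collected as medical history. The exclusion is not written down, though, and one sentence would settle it.

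**Precision against representativeness.** An older height describes an earlier period of growth. This stands: the most recent height has the largest reading error but not necessarily the largest total error. Any minimum interval is a trade-off, and 6 months is a judgment on a smooth curve.

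**Existing safeguards.** Minimum and maximum values, listings and individual growth plots would expose an implausible reference. They would not change the status entered in the tables.

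**Limited reach.** The endpoint is secondary and no hypothesis test is planned. This stands and lowers the priority.

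**Text not seen.** The case report form and the part of SAP 4.4 between 4.4.3 and 4.5 were not available, so a rule there cannot be excluded.

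**Conclusion.** The point holds as a cheap improvement of lower priority. The scaling of error with 12/gap follows from the SAP formula alone. The SDs also need an assumed reading error, and the misclassification rates rest further on assumed growth paths.

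The documents do not support two further inferences. One is that the rule would create a spurious link between antibodies and attenuation: error in a pretreatment reading is probably unrelated to later antibody status, so it would blur the cross-tabulation. The other is that a 6-month minimum cures the problem: at e = 0.3 the borderline child is still missed about a quarter of the time (27%). The primary endpoint and criterion (2) are unaffected.

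**What to change.** Before database lock:

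1. In SAP 4.3 and 4.4.2, define the reference as the most recent historical height obtained at least 6 months before baseline. State that screening-visit heights are not historical. List or flag references based on very old heights.
2. If no height qualifies, treat criterion (1) as missing under SAP 4.7, and say that this overrides the residual No category in 4.4.2.
3. Keep the protocol's combined endpoint, which joins the two criteria with an or. A child at 2 cm/yr or less stays a Yes in the combined proportion and the cross-tabulation, whether or not criterion (1) is evaluable. Restricting those tables to children evaluable for both criteria would conflict with the protocol.
4. Report criteria (1) and (2) separately as well, each with its own denominator. This shows that a child without a qualifying height can count in the combined figure only through criterion (2).
5. Report the distribution of the gap and the number of children without a qualifying height. Repeat the attenuation tables with the present last-height definition as a sensitivity analysis.

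**Cost.** SAP wording and a few table rows; the formula already needs the dates. If only one prior height was collected, the minimum applies to that height. Some children become not evaluable for criterion (1), a number the documents do not allow to be estimated, and an older reference may represent recent pretreatment growth less well.
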